7.2. Patient Disposition

The number and percentage of screen failure patients (ie, patients who entered the Screening Period but not the Pretreatment Period), the number and percentage of pretreatment failures (ie, patients who entered the Pretreatment Period but were not randomized), along with the associated reasons for failure, will be tabulated overall for the Screened Population. Patients who initially failed screening and were re-screened will only be counted once, that is, the PID used for the rescreened patients will be listed for patient disposition, while the PID assigned for the original screening will not be analyzed or listed.

The number and percentage of randomized patients who were included in the Safety Population, who were included in the mITT Population, who completed the Treatment Period, and who prematurely discontinued treatment will be presented overall and by treatment group. A patient is considered to have completed the Treatment Period if the patient completed the 8 weeks of treatment and the EOT Visit that was recorded on the end-of-treatment eCRF page. The reason for premature discontinuation as recorded on the eCRF will also be summarized by treatment group and overall.

The number and percentage of patients who prematurely discontinued treatment will be presented for each treatment group by time of discontinuation, defined as the week (Week 1 through Week 8) in which the treatment discontinuation occurred.

The number of patients screened, the number and percentage of patients randomized will be presented by study center within each geographic region (See Appendix 3 for the definitions of

the geographic regions). A separate disposition table will be generated to include the SA Population and other relevant information.

7.3. Demographics and Other Baseline Characteristics

Demographic parameters (age, age group, race, ethnicity, sex), baseline characteristics (weight, height, and BMI that calculated as weight in kg/[height in m]²), will be summarized descriptively for the Safety, mITT and SA Populations by treatment group and overall.

Baseline efficacy parameters and randomization stratification variables (including EE status, WHSS and its category [3 vs. \geq 3], WRFS, proportion of heartburn-free days, the weekly score of each mRESQ item, sleep disturbance, symptom bothersomeness, and degree of symptom relief) will be summarized descriptively for the mITT and SA Populations by treatment group.

There are several different data derivations for baseline WHSS (Section 5.2.1) and EE status (Section 5.4), the baseline values for each of them will be reported separately for the mITT and SA Populations.

7.4. Compliance

7.4.1. Treatment Compliance

Compliance with study drug dosing (IW-3718 or matching placebo) is defined as the total number of tablets taken by a patient during the study divided by the number of tablets that were expected to be taken, multiplied by 100. The total number of tablets taken will be calculated based on the following formula:

total number of tablets dispensed – (number of tablets returned + number of tablets lost)

The number of tablets lost is recorded on eCRF. The total number of tablets expected to be taken during the study equals the number of days in the study times 6 (minus 3 if the date ends on the day of EOT Visit).

The study drug compliance data will be reported using descriptive statistics for the Safety Population by treatment group. The compliance data will be categorized for increment of 20%, and it will be presented using patient counts and percentages for the Safety Population by treatment group. Additionally, compliance to PPI for the Pretreatment Period and for the Treatment Period will be summarized respectively similarly as the study drug.

7.4.2. eDiary Compliance

Patients are required to enter their diary assessments into the eDiary before bed each night, except assessment of sleep disturbance that is assessed upon getting up each morning during the Pretreatment and Treatment Periods. A daily report is considered complete if all questions in both the morning diary and evening diary (excluding the weekly assessments) are answered, with the following exceptions:

- For the first day of the Pretreatment Period, only the evening diary is expected.
- For the last day of the Pretreatment Period, only the morning diary will be used.
- For the first day of the Treatment Period, only the evening diary will be used.
- For the EOT Visit day, only the morning diary is expected.

eDiary compliance will be calculated for baseline (the Pretreatment Period), the Treatment Period, and weekly within the Treatment Period. For each period, eDiary compliance will be calculated as the number of completed daily reports divided by the expected number of daily reports in the period multiplied by 100.

The eDiary compliance data will be reported using descriptive statistics for the mITT Population by treatment group. The compliance data will be classified by increment of 20%, and it will be presented using patient counts and percentages for the mITT Population by treatment group. Additionally, categorized (≥ 4 vs. <4) weekly eDiary data will be presented using patient counts and percentages by treatment group for the mITT Population.

7.5. Extent of Exposure

Exposure to study drug will be calculated as the number of days from the date of first dose taken to the date of last dose taken in the Treatment Period:

Treatment Duration = Date of last dose of study drug - Date of first dose of study drug + 1

Exposure to study drug for the Safety Population during the Treatment Period will be summarized descriptively by treatment group. Treatment duration will also be categorized as (in days):

- 1
- >1 to ≤ 7
- >7 to ≤ 14
- >14 to ≤ 21
- >21 to ≤ 28
- >28 to ≤ 35
- >35 to ≤ 42
- >42 to ≤49
- >49 to \leq 56 and
- >56

The number and percent of patients in each category will be presented by treatment group for the Safety Population.

Patient-years, defined as total exposure days to the study drug across all patients and divided by 365.25, will be summarized for the WI-3718 group for the Safety Population.

Additionally, exposure to PPI for the Pretreatment Period and for the Treatment Period will be summarized, respectively, similarly to the study drug.

7.6. **Protocol Deviations**

Protocol deviations and Important Protocol Deviations (IPD) will be identified and documented for all randomized patients prior to unblinding through programmatic checks of the study data and select individual data reviews. IPDs will be determined based on a blinded review of all protocol deviations and protocol deviation categories prior to database lock and unblinding; this review will be performed by members of the Ironwood Clinical Trial team, including but not limited to the Study Program Manager, Clinical Medical Monitor. and Study Biostatistician.

The number and percentage of patients with IPDs will be presented by treatment group and IPD category for the Randomized Population. Protocol deviations and IPDs will be provided by patient in data listings for the Randomized Population.

A separate summary and listing of all inclusion/exclusion criteria deviations will also be provided. This summary will be based on data as recorded on the inclusion/exclusion page of the eCRF.

7.7. Prior and Concomitant Medication

Patient's daily eDiary recording of PPI administration will not be reported as a prior or concomitant medication. Instead, it will be summarized separately. Details are specified in Section 7.4.1 and Section 7.5.

Prior medication is defined as any medication started before the date of the first dose of study drug.

Concomitant medication is defined as any medication with a start date prior to, or on the date of the first dose of study drug and continuing after the first dose of study drug, or with a start date between the dates of the first and last doses of study drug, inclusive. Any medication with a start date after the date of the last study drug will not be considered a concomitant medication.

Both prior and concomitant medications will be coded by drug name and therapeutic class using WHO Drug dictionary B2 format, March 2018 version or above. The use of prior and concomitant medications will be summarized for the Safety Population as the number and percentage of patients in each treatment group receiving each medication within each therapeutic class. If a patient took a specific medication multiple times or took multiple medications in the same category (based on Anatomical-Therapeutic-Chemical classification), that patient would be counted only once for the coded drug name or therapeutic class. The use of per-protocol rescue medicines is collected separately in the eDiary (Section 7.8).

7.8. Rescue Medicine Use

During the Pretreatment and Treatment Periods, patients may use dispensed, protocol-permitted rescue medicine when their heartburn becomes intolerable. Patients will report the frequency of their use of rescue medicine (liquid antacid) in the evening eDiary before bed for the day. Overall daily use of rescue medicine will be summarized for each treatment week by treatment group for the Safety Population.

7.9. Efficacy Analysis

The final efficacy analysis will be based on the mITT, while the SA Population will be used for the sensitivity efficacy analysis, and the analyses will be conducted according to the treatment assigned. Baseline values for efficacy parameters are defined as:

- For change from baseline continuous parameter and derived dichotomized response variables, the baseline will be derived from the eDiary and/or eCRF data collected for the last week of the Pretreatment Period (or Week -1), specifically the period from 7 days prior to the day of randomization.
- A time dependent proportion efficacy parameter that is defined as days the event of interest occurs, divided by the number of diary entry days during the relevant period. Its baseline period is the last 14 days (Week -2 to Week -1) prior to day of randomization.

For the change from baseline and response variables, if data for Week -1 are not available, data for Week -2 (the second last week of the Pretreatment Period) will be used.

For responder parameters derived from daily eDiary assessments, a patient who missed 4 or more daily assessments an analysis week will be consider a missing for that week and will be defined as a non-responder for that week. For continuous efficacy parameters, the analysis value for an analysis period is defined as the average of the non-missing values during that period (Appendix 1). If a patient who reported assessments for fewer than 1 day during a week within the Treatment Period, the average is missing for that week. For efficacy parameters no further imputation will be performed (see Section 7.9.1.3 for sensitivity analyses employing multiple imputation [MI] methods). Any efficacy assessments measured after the last dose date will not be included for analysis.

All primary and secondary efficacy parameters are listed in Table 4 will be tested in the given order to protect the overall family wide alpha level at 5%. The mITT Population will be used for the final analysis for all efficacy parameters. The SA Population will be used for the efficacy sensitivity analysis that include selected efficacy parameters at completion of the study.

7.9.1. Primary Efficacy Parameter

7.9.1.1. Estimands

The primary efficacy estimands that are prepared to support regulatory decisions, are described below.

The **While on Treatment Strategy** for the primary efficacy parameter will be used. It is defined by the following:

- Treatment: intervention IW-3718 (1500 mg), while receiving PPIs.
- **Population**: patients in the mITT with GERD who continue to have persistent symptoms, such as heartburn and regurgitation, while receiving once-daily (QD), standard-dose PPIs.

- Variable: Weekly Heartburn Severity Score (WHSS) derived for each treatment visit. The WHSS for a week is the average of the non-missing Daily Heartburn Severity Scores (DHSS) for that week.
- **Intercurrent event**: the following intercurrent events will be considered:
 - a. Discontinuation of treatment due to lack of efficacy
 - b. Lost to follow-up
 - c. Discontinuation of treatment due to AE
 - d. Discontinuation in the study by physician's decision
 - e. Withdrawing consent
 - f. Withdraw due to protocol violations
- **Population-level summary**: mean difference in change from baseline between treatment groups.

Henceforth, for simplicity, background therapy PPIs will be omitted when referring to study drug treatment (IW-3718 and placebo).

7.9.1.2. Analysis of the Primary Efficacy Parameter

The primary efficacy parameter of the study is defined as the change from baseline in WHSS at Visit 5 (Week 8):

- The WHSS for a week is the average of the non-missing Daily Heartburn Severity Scores (DHSS) for that week (Appendix 1).
- The DHSS for a day is the greater score of the 2 mRESQ-eD items assessing heartburn severity ("Burning feeling behind the breastbone or in the center of the upper stomach" and "Pain behind the breastbone or in the center of the upper stomach") for that day. Where one of the 2 mRESQ-eD heartburn severity items is missing for the day, the maximum will be the score of the remaining item; where if both of the items are missing for the day, the DHSS will be missing.

The primary efficacy parameter will be analyzed using a linear mixed-effects model for repeated measures (MMRM). The model will include WHSS change from Baseline at postbaseline scheduled visits up to Week 8 as dependent variable; treatment, randomization stratification variables Baseline EE status (present versus not present) and Baseline WHSS severity level (<3 versus \geq 3), Week (as a categorical variable), Week-by-treatment and Week-by-Baseline WHSS interactions as fixed effects; Baseline WHSS as a continuous covariate; and subject as a random effect. The Kenward-Roger approximation will be used to estimate denominator degree of freedom and adjust standard errors. An unstructured covariance matrix will be used for the MMRM analysis. In the case that the convergence is an issue, the compound symmetry covariance structure will be used. Least square (LS) mean for each treatment group, LS mean difference between the IW-3718 group and the placebo group and a 95% CI for the difference, as well as the *P* value for comparison versus placebo will be presented. For this analysis, the primary contrast of interest is at Visit 5 (Week 8) for IW-3718 compared with placebo.

A corresponding line graph of LS mean with 95% CI by treatment group and Week will be presented. Cumulative distribution function (CDF) of change from baseline at Week 8 in WHSS to be plotted by treatment group. To aid in the interpretation of the graphical representation of the CDF across treatment group, a 2-sample Kolmogorov-Smirnov test will be conducted. If the *P*-value of the Kolmogorov-Smirnov test is small, conclude that the two treatment groups were sampled from populations with different distributions. The populations may differ in median, variability, or the shape of the distribution.

CDF plots of change from Baseline at each week in WHSS by treatment group and patientreported weekly Degree of Relief Assessments (comparing the symptoms over the past 7 days, Appendix 7) classified anchor will be provided. For a sense of variability in the distribution of the classified heartburn relief anchor category, percentile (10th, 25th, 75th and 90th) of change from Baseline to each week in WHSS by treatment group and the anchor will be tabulated.

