6.3. Handling of Dropouts/Missing Data Imputation Method

The WHSS (Section 7.9.1.2) is the average of non-missing Daily Heartburn Severity Scores (DHSS) for the week (Appendix 1). If a patient who reported DHSS for fewer than 1 day during a week within the Treatment Period for a given week, then WHSS is missing for that week.

The WRFS (Section 7.9.2) for a week is the average of the non-missing Daily Regurgitation Frequency Scores (DRFS) for that week (Appendix 1). If a patient who reported DRFS for fewer than 1 day during a week within the Treatment Period for a week, then WRFS is missing for the week.

For responder parameters, OHR (Section 7.9.2), a patient who reported daily symptom severity scores for fewer than 4 days during a week within the Treatment Period will be considered a non-responder for that week. A patient will be deemed a weekly non-responder for all weeks following the patient's discontinuation from the study.

Unless stated otherwise, missing data will not be imputed for any of the efficacy parameters.

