7.9.1.3. Sensitivity Analysis Based on Multiple Imputation – Missing Not at Random (MNAR)

The analysis specified in this section will be executed only when a superiority result that favors the active treatment group for the primary efficacy parameter is obtained.

To characterize the extent of missing data associated with the primary efficacy parameter, the number and percentage of patients with missing evening diaries will be presented by treatment group for the mITT Population for each week of the Treatment Period.

The primary efficacy analysis (MMRM) relies on the assumption that the missing data mechanism follows the missing at random (MAR) scenario. In this case, it is assumed that the reason for data being missing may depend on observed data, but not on the unobserved missing data. The likelihood based MMRM analysis is an appropriate method for the statistical analysis under MAR assumption.

The following sensitivity analysis model, which are within the pattern-mixture model framework, will be used to examine the robustness of the primary efficacy analysis results for the missing not at random (MNAR) mechanisms. Under MNAR, it is assumed that the reason for data being missing is related to the unobserved missing data.

The imputations are based on the distribution of placebo group responses over time. The underlying assumption is that the missing data for a patient on the active treatment follow the distribution of the placebo responses, i.e., the mean values and intra-subject correlations based on the placebo responses will be applied. Moreover, the intercurrent events will generate MNAR (informative) missing, which will have impact on determining of drug effect. A designated penalty will be prespecified for this type of missing mechanism, in order to adjust the treatment effect estimation to determine a possible "true" treatment effect.

The model is implemented in 4 steps:

Step 1: Imputations

For change from baseline data, a total of 200 sets of posterior mean and co-variance estimates are extracted from the available non-missing placebo data. One hundred of the posterior sets will be applied to the pooled active treatment group, while the other 100 will be applied to the placebo group. One set of imputations for all missing values will be generated based on each variation of posterior estimates. All 100 datasets for imputations within a treatment group will be

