ordered from 1 to 100 and combined between pooled active treatment group and placebo, for a total of 100 completely imputed datasets.

Step 2: Adjustments

For patients who have any intercurrent events, a penalty will be designated to the imputed values at the last scheduled visit (Visit 5, Week 8). The penalty is applied to the 2 treatment arms by adding a fraction of the estimated SD for the primary efficacy parameter (the square root of the estimated element for the last scheduled visit of the co-variance matrix R from the primary MMRM model): $(0 \times SD)$, $(0.25 \times SD)$, $(0.50 \times SD)$.

Step 3: Analysis of Complete Datasets

The primary efficacy parameter will be analyzed for each of the 100 complete datasets with imputed and the designated penalty applied data at the last scheduled visit (Visit 5, Week 8), using an analysis of covariance with treatment group as factors and the baseline value as a covariate.

Step 4: Inference

Rubin's Rules will be applied to pool the desired statistical quantities that include LS mean difference estimates, associated 95% CI and p-value, and associated SEs.

Efficacy conclusion of the study is based on the analysis described in Section 7.9.1.2. In the current section, a different missing mechanism is assumed for the data, it is a supportive outcome for the primary efficacy effect analysis.

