7.9.2.1. Analysis of the Secondary Efficacy Parameters

If the primary efficacy comparison generates a superiority result for IW-3718, the secondary efficacy parameters will be tested and so on. The testing order and analysis methods are listed below:

Order of Hypothesis Testing	Parameters	Analysis Method and Outputs	Assumptions
1	Change from Baseline at Week 8 in WRFS	Efficacy parameter WRFS will be analyzed using the MMRM approach like the primary efficacy parameter, WHSS change from baseline.	MAR
2	Overall Heartburn Responder	The proportions of responders between the IW-3718 group and the placebo group will be compared using a Cochran-Mantel-Haenszel (CMH) test controlling for baseline EE status (present vs. not present), baseline WHSS (<3 vs. \geq 3). The CMH test is the primary analysis for responder parameters. The estimated odds ratio (IW-3718 over placebo) associated 95% CI and P value based on CMH test will be tabulated. Additionally, difference in responder rate with a 95% Newcombe CI (3) will also be provided.	Missing will not be imputed.
3	Proportion of Heartburn-free Days During the 8-week Treatment Period	The data will be analyzed using the Poisson regression, which is appropriate for count data. The analysis includes the fixed categorical effect of treatment, the baseline esophagitis status (present vs. not present) and baseline WHSS ($\langle 3 vs. \geq 3 \rangle$), the covariate of baseline proportion of heartburn-free days, and with the diary entry duration (in days) as a weight variable ^a adjusted in the model. Model estimates in difference of incidence rate between the IW-3718 treatment group and placebo will be represented with corresponding 95% CI and P -value associated with the comparisons to placebo. In the case of overdispersion, a negative binomial model instead of Poisson regression will be implemented.	Data following a Poisson distribution. Missing data will not be imputed.

 Table 6:
 Analysis and Assumptions of the Secondary Efficacy Parameters

a. The weight variable weights the overdispersion parameter, which has the default value of 1. The weight variable does not have to be an integer, if it is less than or equal to 0 or if it is missing, the corresponding observation is not used for modeling analysis.

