Appendix 1.Missing Data Simulation to Support the Key Efficacy
Parameters Scoring Algorithm

A missing data simulation study was conducted to assess the impact of the missing data on the scoring algorithm of the key efficacy parameters. The following assumptions were made for the simulation:

- Patients with evidence of pathological acid reflux (positive Bravo status) at baseline in Study ICP-3718-202 represent a study population that is similar to the current study population.
- The efficacy parameters WHSS, WRFS and PHFD in the current study follow the same underlying data distribution as in Study ICP-3718-202.

In Study ICP-3718-202, 45 patients with a positive Bravo status at baseline had non-missing daily assessments in the placebo and IW-3718 1500 mg BID groups combined. The daily assessments were used to derive the efficacy parameters WHSS, WRFS and PHFD. These 45 patients were used for the simulation study.

In Study ICP-3718-202, approximately 10% of patients prematurely discontinued from the study. In the initial simulation, it was assumed that 10% of patients had a given number of missing daily data at each week (ie, the missing data rate). In a second simulation, it was assumed that 20% of patients had a given number of missing daily data at each week.

Daily Scores

Derivation of PHFD is based on Item #1 of mRESQ-eD (Appendix 5). The simulations were run on the value of Item #1.

The daily score that is used to derive the WHSS is the greater score of Item #1 and Item #2 of the mRESQ-eD, which both assess heartburn severity for a given day.

Similar to the WHSS, the daily score that is used to derive the WRFS is the greater score of Item #6 and Item #7 of the mRESQ-ed, which both assess regurgitation frequency for a given day.

It was assumed that a scenario whereby a patient misses 1 of the 2 mRESQ-eD items does not occur. The reason is that when a patient answers a mRESQ-eD question, the next question automatically appears on the device, and it cues the patient to answer that question. Given the nature of the device, there are most likely only 2 scenarios for the mRESQ-eD data collection: 1) a patient answers all mRESQ-eD items; 2) none of the items are answered. The experience of Study ICP-3718-202 supports this. There was no instance where the eDiary had partial data for a given day. Similarly, this has been the experience in the 2 ongoing Phase 3 studies.

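### Low priority: the primary MMRM's only convergence fallback, compound symmetry, would understate the Week 8 standard error if variances rise as in SAP Tables 11 and 12, and its trigger is undefined

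*SAP*

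**What the plan says.** - **Primary model (SAP 7.9.1.2).** Change in WHSS over eight weeks, unstructured covariance, Kenward-Roger standard errors and degrees of freedom. The contrast of interest is Week 8.
- **Fallback (same section).** "In the case that the convergence is an issue, the compound symmetry covariance structure will be used". No other structure is listed and the trigger is not defined. Protocol 3.7.4.3 specifies unstructured covariance and no fallback.
- **Random term (same section).** The model also has "Baseline WHSS as a continuous covariate; and subject as a random effect".
- **First key secondary (SAP 7.9.2.1, Table 6).** "Efficacy parameter WRFS will be analyzed using the MMRM approach like the primary efficacy parameter, WHSS change from baseline". WRFS therefore inherits the fallback.
- **Missing weeks (SAP 6.3).** A week is lost only when the patient "reported DHSS for fewer than 1 day during a week within the Treatment Period for a given week, then WHSS is missing".
- **MNAR analysis (SAP 7.9.1.3).** It "will be executed only when a superiority result that favors the active treatment group for the primary efficacy parameter is obtained". Its penalty SD is "the square root of the estimated element for the last scheduled visit of the co-variance matrix R from the primary MMRM model", and "The penalty is applied to the 2 treatment arms by adding a fraction of the estimated SD for the primary efficacy parameter".
- **Error control (SAP 6.6).** A fixed sequence holds the family-wise rate at 5%.

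**The concern.** Compound symmetry fits a single variance, in effect the average over the eight weeks. If the true variance is highest at Week 8, the Week 8 standard error comes out too small and the test rejects too often. Kenward-Roger does not repair this, because it takes the fitted structure as true. The first two tests in the sequence would both be affected. Because the trigger is loosely worded, the switch would also leave a discretionary choice inside the primary test.

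A related wording problem bears on how likely the switch is. An unstructured residual matrix plus a separate random subject effect has one covariance parameter too many. That redundancy could produce the warning that sends the analyst to the fallback. It also leaves the Week 8 element of R, from which the MNAR penalty is taken, without a unique value.

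**Working it through.** **1. The plan's own figure.** SAP Table 1: difference 2.01 − 1.58 = 0.43; SD = sqrt((1.20² + 1.29²)/2) = 1.246; 330 per arm. SE = 1.246 × sqrt(2/330) = 0.097; power = Φ(0.43/0.097 − 1.96) = 99.3%. The stated 99% is reproduced.

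**2. Size if compound symmetry is used, complete data.** Inputs are the weekly SDs of change without missing data.
- WHSS (Table 11): 1.04, 1.13, 1.18, 1.24, 1.30, 1.22, 1.29, 1.34
- WRFS (Table 12): 0.76, 0.93, 1.02, 1.06, 1.06, 1.00, 1.04, 1.11

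Ratio of fitted to true Week 8 SE = sqrt(mean weekly variance) / Week 8 SD. Type I error = 2 × (1 − Φ(1.96 × ratio)).
- WHSS: sqrt(1.4908) = 1.221; 1.221/1.34 = 0.911; type I error 7.4%
- WRFS: sqrt(1.0055) = 1.003; 1.003/1.11 = 0.903; type I error 7.7%

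The standard error is 9-10% too small.

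**3. The same with the 94-patient Week 8 SDs.** Pooling SAP Table 1 (43 and 51 patients) gives 1.250 (WHSS) and 1.011 (WRFS). Substituting these at Week 8 only, which mixes two samples, gives ratios 0.967 and 0.979 and type I error 5.8% and 5.5%.

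**4. With 10% dropout.** SAP Appendix 1 reports about 10% discontinuation in Phase 2b. The correlations are assumptions: constant at 0.6 or 0.8, or autoregressive at 0.8 or 0.9. Comparing model-based with true variance under monotone dropout gives:
- WHSS 7.5-8.0%, or 5.9-6.3% with the 94-patient SD
- WRFS 7.8-8.3%, or 5.6-6.0% with the 94-patient SD

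A REML simulation for WHSS (550 patients, 4,000 trials, correlation falling linearly from 0.85 to 0.55) gave 7.7%, Monte Carlo SE 0.4 points.

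**5. Chance of fallback.** No document gives one. An unstructured 8 × 8 matrix has 8 × 9/2 = 36 parameters. In 1,000 simulated trials of 550 patients with 10% dropout and an assumed 3% of weeks missed, all fits converged; the 95% upper bound on failure is 1 − 0.05^(1/1000) = 0.3%. Those fits used maximum likelihood rather than SAS REML, and left out the strata and the separate random subject effect.

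**6. The random subject term.** A random intercept with variance c adds c to every element of the covariance matrix, and an unstructured R can absorb that exactly. The model then has 37 parameters, and the information matrix has rank 36. The Week 8 contrast is unchanged, but the split between c and R is arbitrary.

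**7. Overall type I error** = 5% + P(fallback) × (conditional rate − 5%). For assumed probabilities of 5%, 10% and 25%:
- at 7.66%: 5.13%, 5.27%, 5.67%
- at 8.3%: 5.17%, 5.33%, 5.83%

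At the 0.3% bound and 7.66% it is 5.01%.

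**8. MNAR penalty, 0.50 × SD.**
- R holds everything, unstructured: 0.5 × 1.34 = 0.67
- R holds everything, compound symmetry: 0.5 × 1.22 = 0.61
- Compound symmetry through a random intercept (assumed average correlation 0.75), R holds the residual only: 0.5 × 0.61 = 0.31

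The widest gap, 0.5 × (1.34 − 0.61) = 0.365, multiplied by an assumed 2-, 5- or 10-point imbalance in intercurrent events, moves the treatment difference by 0.007, 0.018 or 0.037. That is 1.7%, 4.2% or 8.5% of 0.43.

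**9. Check on the remedy.** With model-based errors, heterogeneous Toeplitz gave 5.0% under constant and autoregressive correlation but 6.3% under an assumed random-slope pattern. Heterogeneous compound symmetry ranged from 3.8% to 5.4%. In simulations with 10% dropout where compound symmetry gave about 8%, sandwich errors gave 5.7% (Monte Carlo SE about 0.6 points).

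**The case against.** **The fallback will almost never be used.** This largely stands. With about 550 patients, 36 parameters and a weekly score that needs one diary day, the unstructured model should fit. The convergence runs did not include the literal random subject effect, though, so they say nothing about a warning from that source.

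**The inflation is not established.** This stands in part. Appendix 1 says "45 patients with a positive Bravo status at baseline had non-missing daily assessments", with both arms combined, and the SDs are not adjusted for baseline. One SD from 45 patients has a relative standard error of about 1/sqrt(2 × 44) = 11%, similar to the 9-10% shortfall. Weekly scores are correlated, which makes the ratio more precise than that, but a ratio near 1 is not excluded. Baseline adjustment can move it either way. Under assumed slopes (baseline SD 0.6-0.9), conditional type I error at 0-10% dropout was about 5.2-7.5% if the slope grows over weeks and about 7.5-8.4% if it is constant.

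**Compound symmetry with sandwich errors would restore the size in large samples.** This is true when data are missing completely at random. Under MAR dropout, which the primary analysis assumes, sandwich errors do not remove bias in the means from a wrong covariance. That is the reason to put week-specific variances first.

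**The penalty SD is already defined.** This is correct: SAP 7.9.1.3 defines it. What needs clarifying is what R contains.

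**Conclusion.** A cheap improvement of low priority. If the fallback is used and variances rise as in Tables 11 and 12, type I error for the first two tests is about 7.4-7.7% with complete data and about 7.5-8.3% with 10% dropout; with the 94-patient Week 8 SDs it is about 5.5-6.3%. These figures depend on Phase 2b SDs, assumed correlations and dropout unrelated to outcome.

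A reader might infer that the primary test will run at 7-8%, or that the 5% control in SAP 6.6 fails. The documents do not support either. The inflation is conditional on an event that is unlikely under the unstructured model alone, where overall error stays near 5.0%. Nor is there a firm ceiling on overall error, because no document gives a fallback probability and the values used above are assumptions.

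The penalty point does not bear on type I error. It concerns a supportive analysis that runs only after a positive primary result and penalises both arms, so its effect is zero if intercurrent events are balanced. Phase 2b discontinuations for TEAEs were 3 on placebo and 3 on 1500 mg (Protocol 1.3).

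**What to change.** Amend SAP 7.9.1.2 before unblinding:
- Delete the random subject term, or state that it only names the subject for the repeated measures.
- Define non-convergence.
- Replace the sole compound-symmetry fallback with an ordered list that keeps week-specific variances, for example heterogeneous Toeplitz and then heterogeneous compound symmetry. Use sandwich standard errors and a named degrees-of-freedom method at any fallback step.
- Apply the rule to WHSS, WRFS and the other MMRMs.

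In SAP 7.9.1.3, state that the penalty SD is the square root of the total marginal Week 8 variance from the fitted primary model.

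The cost is a short wording change and a noted difference from Protocol 3.7.4.3 and the synopsis. Kenward-Roger gives way to another method only if a fallback step is used. No new data are needed and the planned unstructured analysis is unchanged.
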